### 7.10.3 Exploratory endpoints not covered by this SAP

A large grid of black bars on a white background, representing a heavily redacted document. The grid consists of approximately 20 horizontal rows and 10 vertical columns of varying bar lengths. Some rows have a single long bar, while others have multiple shorter bars. The pattern is irregular, suggesting a random or systematic redaction process. The bars are solid black and have thin white borders.

## 7.11 Safety

As described in Section 5.1, the SAF will be the basis for the analysis of safety data. Some additional summary tables will be given for the 3-by-3 Evaluable Population. If this is the case, these will be stated below. Cohorts evaluated for safety analyses are described in Section 7.1.1. For safety laboratory no tables for Cohort 1 will be provided.

### 7.11.1 Study drug exposure and compliance

The duration of study drug exposure will be calculated separately for EO2401 and nivolumab and is defined in months as

$$(last\ treatment\ date - first\ treatment\ date + 1)/30.5$$

(rounded to one decimal). The duration of study drug exposure will be summarized using basic summary statistics, by cohort. Additionally, the duration of exposure will be summarized by cohort using the following categories:

- $\leq 3$  months
- $> 3$  and  $\leq 6$  months
- $> 6$  and  $\leq 12$  months
- $> 12$  months.

The number and percentages of patients with 0, 1, 2, ... administered doses of EO2401 or nivolumab, with administered doses of nivolumab without interruption, and with full amount of nivolumab administered will be provided. Basic statistics for the total number of EO2401 administrations, the total number of nivolumab administrations, the total number of nivolumab administrations without interruption and the total number of nivolumab administrations during which the full amount was administered per patient will be provided by cohort

### 7.11.2 Adverse events (AEs)

AEs will be coded using the MedDRA dictionary version 27.0.

The investigator could assess the relationship of an AE to both study drugs either individually (i.e. for EO2401 and nivolumab separately) or combined (i.e. for both EO2401 and nivolumab together). In context of the intended study treatment, as composed of administered in combination with nivolumab, it is most of the times in principle not possible to make causality assessments for each component by itself (due to the nature of the combination treatment and the mode of action of the components). Only in rare cases (e.g., an AE that appears in the 3-hour time interval between the first injection of EO2401 and the first infusion of nivolumab or in cases where nivolumab administrations have been terminated but treatment continues with EO2401) an individual assessment seems reasonable.

Hence, an AE related to study treatment is defined as any AE with a suspected relationship to EO2401/nivolumab combined, with a suspected relationship to EO2401 alone or a suspected relationship to nivolumab alone or with no information with respect to relatedness (i.e. NA cases).

According to the protocol an AE is considered to be treatment emergent if it is not present when the active phase of the study begins and is not a chronic condition that is part of the patient's medical history, or it is present at the start of the active phase of the study or as

part of the patient's medical history, but the severity or frequency increases during the active phase. The active phase of the study begins at the time of the first dose of the study drug. The active phase of the study ends [REDACTED] after the last study drug administration. Therefore, the following AEs will be considered as not treatment emergent and will be excluded from summary tables:

- AEs starting more than [REDACTED] after last study drug administration
- AEs occurring in patients not treated with EO2401 and/or nivolumab
- AEs starting prior to first study drug administration for that no deterioration in CTCAE grade was documented during the active phase (e.g. patient for that the CTCAE grade improved only)

The following rules will be applied to identify if an AE is regarded as TEAE in case of missing or incomplete start and/or end dates.

- Partial or missing AE start dates will be imputed as follows:
  - a) Missing day - Impute the 1st of the month unless month is same as month of first dose of study drug then impute first dose date,
  - b) Missing day and month – impute 1st January unless year is the same as first dose date then impute first dose date. If this rule leads to an imputed start date posterior to the end date (after imputation of end date if needed), then impute 1st January for start date rather than first dose date,
  - c) Completely missing – impute first dose date unless the end date suggests it could have started prior to this in which case impute the 1st January of the same year as the end date.
- Partial or missing AE end dates will be imputed as follows:
  - a) Missing day - impute the last day of the month. If the patient died in the same month, then set the imputed date as the death date,
  - b) Missing day and month – impute 31st December. If the patient died in the same year, then set the imputed date as the death date,
  - c) Completely Missing – No imputation.

If a patient is known to have died where only a partial death date is available, then the date of death will be imputed as the latest of the last date known to be alive +1 from the database and the death date using the available information provided:

- a) For Missing day only – using the 1st of the month,
- b) For Missing day and Month – using the 1st of January.

All AE classified as **not** TEAE via programming will be reviewed and confirmed during the DRM meeting.

In case of worsening of an AE, the worst grade (NCI CTCAE v5.0) will be used for the analysis and will be counted as one AE.

An overview table presenting number and percentage of patients and the number of AEs in the following categories will be created for the SAF, by cohort:

- Any AE
- Any TEAE

- Any local administration site conditions at a site of EO2401 local administration (LASR)
- Any TEAE with worst grade 1 (NCI CTCAE v5.0)
- Any TEAE with worst grade 2 (NCI CTCAE v5.0)
- Any TEAE with worst grade 3 (NCI CTCAE v5.0)
- Any TEAE with worst grade 4 (NCI CTCAE v5.0)
- Any TEAE with worst grade  $\geq 3$  (NCI CTCAE v5.0)
- Any TEAE leading to death
- Any disease progression-related TEAE
- Any TEAE related to study treatment
- Any TEAE related to study treatment with worst grade  $\geq 3$  (NCI CTCAE v5.0)
- Any TEAE leading to definitive discontinuation of any study drug
- Any TEAE leading to definitive discontinuation of EO2401
- Any TEAE leading to definitive discontinuation of nivolumab
- Any TEAE leading to interruption of EO2401
- Any TEAE leading to interruption of nivolumab
- Any serious TEAE
- Any serious TEAE related to study treatment

TEAEs, TEAEs related to study treatment, serious TEAEs, serious TEAEs related to study treatment, non-serious TEAEs, LASRs, TEAEs leading to definitive discontinuation of EO2401, and TEAEs leading to interruption of EO2401 will be summarized by the number of events, and the number and percentage of patients, stratified by cohort. In these tables, AEs will be presented by MedDRA PT and grouped by MedDRA SOC. These tables will be sorted by the overall frequency of MedDRA PTs within each MedDRA SOC. An additional table will present TEAEs by MedDRA PT only, and will be sorted by overall frequency of MedDRA PTs.

Furthermore, TEAEs, serious TEAEs, and TEAEs with a worst CTCAE grade of at least 3 will be summarized by the number and percentage of patients per MedDRA SOC and MedDRA PT, stratified by cohort and by worst CTCAE grade. Multiple occurrences of the same AE in the same patient will be counted once using the worst CTCAE grade. In case of missing CTCAE grade the category "missing" will be added. Missing will be counted as the least severe category.

TEAEs [REDACTED] will be summarized by MedDRA PT and grouped by MedDRA SOC for Cohort 1, using the 3-by-3 Evaluable Population.

In addition, time to 1st LASR event will be assessed by a KM-analysis, with censoring if no LASR was reported. If no LASR event was documented, the censoring date will be the date of the latest physical examination with a normal finding for "skin" and "extremities". If no LASR event was documented, and physical examination for extremities was abnormal for baseline and all post-baseline visits, but no change compared to baseline was documented for the post-baseline visits, the censoring date will be the date of the latest physical examination. If no LASR event was documented, and no post baseline

physical examination assessment is available, the censoring date will be the date of first study treatment. If no LASR event was documented, physical examination for "skin" and "extremities" was normal at baseline, but abnormal post-baseline, the censoring date will be the date of first study treatment. The duration of all LASR events will be assessed by a KM-analysis, with censoring if there is no end date reported. The censoring date will be the date of the latest physical examination with an abnormal finding for "skin" or "extremities". If the end of LASR date is given partial only, the rules for incomplete end dates defined above will be used. Time to 1st LASR, and duration of all LASR events will be described by KM plots. Separate plots will be created including the curves of following cohorts:

- Cohorts 2A, 2B, 3A, and 3B, non-randomized
- Cohorts 2A, 2B, and 2, non-randomized
- Cohorts 3A, 3B, and 3, non-randomized
- Cohort 2A-I, Cohort 2A-II, and Cohort 2A-III, randomized.

The median, as well as 1st and 3rd quartiles of the estimated times of interest will be presented with their associated two-sided 95% CIs according to Klein and Moeschberger using a log-log-transformation.

All AEs, all serious AEs, all LASR, all AEs leading to death, all AEs related to disease progression, all TEAEs leading to definitive termination of EO2401 or of nivolumab, all TEAEs leading to interruption of EO2401, and all TEAEs leading to interruption of nivolumab will be listed in separate by-patient listings. One AE listing will include all details of changes in CTCAE grades for those AE, where changes in CTCAE grade were documented.

TEAEs with a suspected relationship to EO2401 alone and TEAEs with a suspected relationship to nivolumab alone will be presented in separate by-patient listings.

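### AE start-date rule (a) in SAP 7.11.2 ignores the end date, so an event that ended before first dose can be counted as treatment-emergent

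*SAP*

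**What the plan says.** SAP 7.11.2 introduces its date rules with their purpose: "The following rules will be applied to identify if an AE is regarded as TEAE in case of missing or incomplete start and/or end dates". Three start-date rules follow.

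- Rule (a), day missing: "Impute the 1st of the month unless month is same as month of first dose of study drug then impute first dose date". The end date is not mentioned.
- Rule (b), day and month missing: 1 January, or the first-dose date if the year matches. It then has a guard, beginning "If this rule leads to an imputed start date posterior to the end date (after imputation of end date if needed", which falls back to 1 January.
- Rule (c), wholly missing: "impute first dose date unless the end date suggests it could have started prior to this", in which case 1 January of the end-date year is used.

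TEAE status then turns on the start date. On the pre-treatment side, the SAP removes from the summary tables "AEs starting prior to first study drug administration for that no deterioration in CTCAE grade was documented during the active phase". The end date plays no part in that exclusion. The boundary is first dose: "The active phase of the study begins at the time of the first dose of the study drug".

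The manual check covers AEs classed as not "TEAE via programming will be reviewed and confirmed during the DRM meeting".

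On severity the section says: "In case of worsening of an AE, the worst grade (NCI CTCAE v5.0) will be used for the analysis". It gives no time window.

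Rule (a) appears in the same form for medications (SAP 7.6) and for procedures (SAP 7.7).

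**The concern.** Moving an uncertain start to the first-dose date is a normal conservative choice when the event might have begun on treatment. It is not conservative when the recorded end date shows that the event was over before treatment began. Rule (a) does not separate the two cases, so it can produce an event that starts after it ends and attribute it to study treatment.

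The ordering is also odd: a record with a known month is handled worse than one with only the year, or with nothing. That suggests an omission rather than a decision.

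AEs are recorded from consent (Protocol 7.3 and 8.3.1), so pre-dose events are in the database. TEAE incidence is part of the phase 1 primary endpoint (Protocol 3.2.1, SAP 4.4.1) and of the safety assessment in the randomized extension (Protocol 3.2.2). SAP 7.11.2 also counts an AE with no relatedness information as related. A misclassified pre-dose AE without that entry would therefore reach the related-TEAE rows too; how often that happens is not stated.

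**Working it through.** **Start-date rules.** The rules were applied literally to one assumed case: first dose 20 March, AE ended 10 March, no worsening on treatment.

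| What is known of the start | Imputed start | Against end date | Class |
|---|---|---|---|
| Month (rule a, as written) | 20 March | 10 days after end | TEAE |
| Year only (rule b) | 20 March, then 1 January by the guard | before end | not TEAE |
| Nothing (rule c) | 1 January | before end | not TEAE |
| Month (rule a with an end-date guard) | 1 March | before end | not TEAE |

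The other rule (a) cases were then run to see whether a guard would disturb them. With the end on 25 March, the end day missing (imputed to 31 March) or the end wholly missing, the start is 20 March and the AE is a TEAE with or without the guard. Only the impossible case changes.

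**Medications and procedures.** Take a drug started in March (day missing) and stopped on 10 March. Rule (a) in SAP 7.6 gives a start of 20 March, which is Day 1.

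- Prior requires start and stop before Day 1. The imputed start fails.
- Concomitant requires a dose between Day 1 and last treatment. The stop on 10 March fails.
- Post-treatment requires a start after last treatment. This fails too.

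The record meets none of the three definitions. A procedure under SAP 7.7 behaves the same way.

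**Size of one misclassified patient.** Treated numbers are from SAP 4.2, assumed to be the safety denominators. The change is 100/n percentage points.

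| Column | n | Change |
|---|---|---|
| Cohort 2A, non-randomized | 26 | 3.8 |
| Cohort 2A-I | 13 | 7.7 |
| Cohort 3B | 5 | 20 |
| Cohort 2A-III | 4 | 25 |
| Cohort 2A-II | 2 | 50 |
| Cohorts 2 + 3 (26 + 7 + 13 + 5) | 51 | 2.0 |

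A percentage moves only if the patient is not already in that row. A preferred-term row can therefore shift while the any-TEAE row does not. The event count rises by one in either case.

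**Worst grade.** Assume one continuous AE with grade 3 before dosing, grade 1 at first dose and grade 2 on treatment. The step from 1 to 2 is a deterioration in the active phase, so it is a TEAE. The maximum over all grades is 3; the maximum within the active phase is 2. The text allows either. SAP 7.11.3 does state its windows for laboratory data: worst values exclude baseline, and worst laboratory grades include pre-treatment assessments.

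**The case against.** The strongest reply is that the trigger is very narrow. It needs an unknown onset day, onset in the calendar month of first dose, and a known end earlier in that month. A patient dosed early in a month has almost no such window. Illnesses present at consent are not AEs (Protocol 7.3), AEs are recorded with onset and end dates (Protocol 8.5.2), and data are queried (Protocol 10.7). The phase 1 endpoint is a descriptive medical assessment with no test, and over-counting TEAEs is the cautious direction. All of this stands, and it makes the point minor. It does not make the rule right, since an event known to be over before dosing is not a doubtful case.

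Three stronger readings are tempting, and the documents do not support them.

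- **Rule (a) turns earlier medication into concomitant medication.** It does not. The stop date still fails the concomitant definition, and the record is left unclassified.
- **Imputation creates PFS events on Day 1.** A reader might note that chemotherapy with year-only start and stop dates in the first-dose year would run from first dose to 31 December and so look concomitant. That is rule (b), not rule (a). SAP 7.6 limits the imputation to deciding concomitant status, and SAP 7.8.1 has non-trial systemic anti-cancer treatments confirmed at the DRM. Exclusion criterion 4 (Protocol 5.2), which bars cytoreductive therapy within 28 days before first EO2401, also makes a stop date known only to the year unlikely.
- **The worst-grade sentence is an error.** It applies to worsening, and the exclusion rule ties deterioration to the active phase, so taking the grade reached on treatment is a natural reading. SAP 7.11.2 also provides a listing of all grade changes. What remains is a missing window.

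**Conclusion.** The gap in rule (a) is real. Read literally, SAP 7.11.2 makes a TEAE of an AE that demonstrably ended before first dose, and the stated review does not look at that group. The direction is one way, towards more TEAEs. The documents do not give the number of affected records; given the three conditions needed, it is probably small. The per-patient effect runs from 3.8 points in Cohort 2A to 50 points in Cohort 2A-II, and applies only where that patient was not already in the row.

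In SAP 7.6 and 7.7 the same rule leaves a record in no category, which is untidy rather than harmful. The worst-grade sentence needs a clarification, not a correction. Nothing here reaches the efficacy endpoints. The conclusion rests on a literal reading of the rules; a programmer might add the end-date check unprompted, but the SAP does not ask for it.

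**What to change.** 1. In SAP 7.6, 7.7 and 7.11.2, add to start-date rule (a): *where the imputed start would fall later than the end date, itself imputed if incomplete, use the first of the month instead.* This extends rule (b)'s guard, with a fallback suited to a missing day.
2. In SAP 7.11.2, state that for TEAE tables the worst grade is the highest grade recorded on or after first dose and within the active phase.

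The cost is one sentence in three places, one further sentence, and small program changes. TEAE status is unchanged wherever the end is after first dose, has only its day missing, or is wholly missing.

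The fix should stop there. A blanket rule that imputed dates cannot create PFS events could discard genuine deaths, or post-study chemotherapy, with partial dates. Excluding prior lines of therapy from the concomitant category would conflict with continued mitotane, which SAP 7.4.2 and 7.6 set out to tabulate.

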  - medical history of other (than oncology) disease processes (all prior significant illnesses that are relevant to patient safety or that the patient has experienced prior to screening; especially history of anaphylaxis or other reactions following vaccination, and history of immune deficiencies), and concomitant illness (illnesses present at the time of informed consent are to be regarded as concomitant illnesses; illnesses first occurring or detected during the study and/or worsening of a concomitant illness during the study are to be documented as AEs on the eCRF and as SAEs if case seriousness criteria are met),
  - medications, including vaccines, and other relevant treatments (e.g. surgeries) during 28 days prior to signing informed consent; all applicable treatments (systemic and local), also before 28 days prior to informed consent signing, for oncology disease(s) will be collected,
  - concomitant medications/treatments,

- measurement/assessment of;
  - height and weight,
  - ECOG performance status (see [Section 12.2](#)),
  - vital signs including temperature, blood pressure (BP), and heart rate (HR) (BP and HR will be measured according to local standard practice); if systolic BP is below 100 mmHg or above 150 mmHg, and/or diastolic BP is below 50 mmHg or above 90 mmHg, the measurement will be repeated; the HR measurement will be repeated when below 50 bpm or above 100 bpm,
  - major body systems via physical examination; general appearance, skin, neck (incl. thyroid), ENT (ears, nose, throat), lungs, heart, abdomen, lymph nodes (all major stations palpable), extremities, neurology, and other sites as applicable (i.e. symptom directed),
- safety blood samples for hematology, coagulation, serum chemistry, urinalysis, hormones, and virus serology to be performed and evaluated locally, detailed as;

A large black rectangular box used to redact sensitive information.

- a 12-lead electrocardiogram (ECG) will be recorded according to local site standard procedures, and
- adverse events will be reported according to NCI-CTCAE v5.0; documentation of AEs/SAEs starts after trial consent has been given by the patient.

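### SAP 7.11.2 censors an undated local reaction at any abnormal skin or extremities exam, so its duration can be zero, negative, undefined or too long

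*SAP*

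**What the plan says.** On LASR duration, SAP 7.11.2 states: "The duration of all LASR events will be assessed by a KM-analysis, with censoring if there is no end date reported". The date is then set as follows: "The censoring date will be the date of the latest physical examination with an abnormal finding for" skin or extremities.

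The date rules in the same section decide which records reach this rule. For a partial end date, "If the end of LASR date is given partial only, the rules for incomplete end dates defined above will be used", so that reaction receives an imputed end. For a fully missing end date the instruction is "Completely Missing – No imputation", so that reaction is censored. The rule therefore governs fully missing end dates only.

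For time to first LASR the same section takes more care. There, "the censoring date will be the date of the latest physical examination with a normal finding for" skin and extremities. A separate branch covers exams that were abnormal throughout, "but no change compared to baseline was documented for the post-baseline visits". If there is no post-baseline exam, the date of first study treatment is used. The duration rule has no counterpart to any of these three provisions.

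**The concern.** The rule looks like a last-known-ongoing date. That would be sound if the abnormal finding were the reaction itself. As worded, three links are missing: the exam need not fall on or after onset, the finding need not be the LASR or new since baseline, and a later normal exam has no effect. There is also no date for a patient who never had an abnormal exam.

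Local reactions are the main anticipated adverse events of EO2401 (Protocol Synopsis). Their duration is to be shown in Kaplan-Meier plots, with median, quartiles and 95% confidence intervals. Invalid or misdated censoring times would feed directly into that output.

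**Working it through.** The plan gives no figure to reproduce here, so the check applies the rule to dates.

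**Inputs**
- Interval: end date − start date + 1 (SAP 6.5).
- Exam days: V1 to V4 every 2 weeks (Protocol 7.4.1) gives days 1, 15, 29 and 43. Boosting starts at Week 11 and repeats every 4 weeks (Protocol 4.2.1), which gives day 10 × 7 + 1 = 71, then 99, 127 and 155. Visit windows are ignored.
- Order: assessments come before same-day dosing (Protocol 7.4), so a reaction to that day's injection starts after that day's exam.
- Content: the exam is of "major body systems via physical examination; general appearance, skin, neck (incl. thyroid" and so on), with extremities as another whole category (Protocol 7.3). It is not an injection-site exam.
- Onset days and findings below are illustrative.

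**A. Date before onset.** The day 43 exam is abnormal from an earlier reaction. The patient is then injected, a new reaction follows, and all later exams are normal.
- Onset day 44: 43 − 44 + 1 = 0 days.
- Onset day 50: 43 − 50 + 1 = −6 days.

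**B. No date.** Onset is day 44, the reaction clears before the day 71 exam, and no exam was ever abnormal. The rule returns nothing.

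**C. Date too late.** Onset is day 16, the day 29 exam is normal, and an unrelated rash is seen on day 155. The rule gives 155 − 16 + 1 = 140 days. The normal exam came at 29 − 16 + 1 = 14 days. A later LASR at another rotated site (Protocol 6.3) would move the date in the same way.

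**D. One date per patient, not per event.** Two undated LASRs start on days 16 and 44, and the latest abnormal exam is day 43. They get 43 − 16 + 1 = 28 days and 43 − 44 + 1 = 0 days.

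**Direction.** Case C keeps a record at risk too long and pushes the curve up. In A and B the record drops out or someone must choose a date. The effect then depends on which reactions lack an end date.

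**Same cases under the rule proposed below**
- A (onset day 50): censored at onset, 50 − 50 + 1 = 1 day. As an interval, the end lies between 1 and 71 − 50 + 1 = 22 days.
- B: censored at 1 day; interval 1 to 71 − 44 + 1 = 28 days.
- C: censored at 1 day; interval 1 to 14 days.

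All are valid. Censoring at onset carries almost no information, which is why the interval-censored analysis is needed as well.

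**The case against.** Data collection should keep such records few. Related AEs are followed until resolved or stabilised (Protocol 8.3.2), each AE record should hold an end date and an outcome where possible (8.5.2), and discrepancies are queried (10.7). An undated LASR should then mostly be one still open. If it is still visible at the last exam, the SAP rule returns that exam, which is correct. The output is also descriptive: no visible efficacy endpoint, test or stopping rule uses it. All of this stands and limits the importance of the point. It does not supply the missing onset condition, link to the reaction or fallback.

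A reader might infer three stronger points, which the documents do not support:
- *LASR duration as a whole is biased upward by a known number of days.* Complete and partial end dates never reach this rule, and the number of undated LASRs is not given. Any figure would mainly restate an assumed share of undated reactions and an assumed true duration. Protocol 1.3.5 expects short reactions.
- *A normal exam proves the reaction ended and should become its end date.* Local pain counts as a local reaction and need not show on a body-system exam. With exams 2 to 4 weeks apart, that rule also overstates short reactions. One running from day 44 to day 50 lasts 7 days, but setting its end at day 71 gives 28.
- *Partial end dates are handled wrongly.* Month-end imputation, or "impute 31st December" when the month is also missing, lengthens durations. It is, however, the SAP's convention for AEs, medications and procedures alike, and it is capped at death. A midpoint would be another convention, not a correction.

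**Conclusion.** The point holds for LASRs with a fully missing end date. The rule as written can give those records a zero, negative or undefined time, or carry one past a normal exam to an unrelated finding. Nothing in the visible text of either document prevents this.

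For a single record the error can be large: −6 and 140 days in the worked cases, which rest on illustrative dates. The effect on the median and quartiles cannot be sized from the documents. It is nil if every undated LASR was still visible at the patient's last exam, and it grows with the number that had resolved without an end date. LASR incidence, the by-patient listings and all efficacy results are unaffected. This is a minor but genuine fault in a descriptive safety analysis.

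**What to change.** Reword the duration rule in SAP 7.11.2 for LASRs with a fully missing end date:
- Use only exams on or after the onset of that LASR. A pre-dose exam on the onset day should not count as a normal exam that closes the reaction.
- Censor at the last abnormal exam before the first exam that is normal for both skin and extremities. Do not count abnormalities recorded as another AE or unchanged from baseline.
- If there is no such exam, censor at onset.
- Where a later normal exam exists, treat the end as interval-censored between the last abnormal exam (or onset) and the first normal exam, at least as a sensitivity analysis. Do not set the end at the normal exam.
- Report the number of undated LASRs by cohort.

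The cost is a few lines of SAP text, a small change to the derivation and one added analysis, all using exam data already collected. Deciding which abnormalities belong to another AE can be done at the data review meeting.
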